#### **8.1.1. Additional Details on Recording Adverse Events on the CRF**

All events detailed in the table above will be recorded on the AE page(s) of the CRF. It should be noted that the CT SAE Report Form for reporting of SAE information is not the same as the AE page of the CRF. When the same data are collected, the forms must be completed in a consistent manner. AEs should be recorded using concise medical terminology and the same AE term should be used on both the CRF and the CT SAE Report Form for reporting of SAE information.

#### **8.1.2. Eliciting Adverse Event Information**

The investigator is to record on the CRF all directly observed AEs and all AEs spontaneously reported by the study subject, legally acceptable representative/parent(s) or legal guardian, if applicable. In addition, each study subject, legally acceptable representative/parent(s) or legal guardian, if applicable, will be questioned about the occurrence of AEs in a non-leading manner.

#### **8.1.3. Withdrawal from the Study Due to Adverse Events (see also the [Subject Withdrawal](#) section)**

Withdrawal due to AEs should be distinguished from withdrawal due to other causes, according to the definition of AE noted below, and recorded on the CRF.

When a subject withdraws from the study because of an SAE, the SAE must be recorded on the CRF and reported, as appropriate, on the CT SAE Report Form, in accordance with the [Requirements](#) section above.

#### **8.1.4. Time Period for Collecting AE/SAE Information**

The time period for actively eliciting and collecting AEs and SAEs (“active collection period”) for each subject begins from the time the subject, legally acceptable representative/parent(s) or legal guardian, if applicable, provides informed consent, which is obtained before the subject’s participation in the study (ie, before undergoing any study-related procedure and/or receiving investigational product), through and including a minimum of 28 calendar days; except as indicated below after the last administration of the investigational product.

For subjects who are screen failures, the active collection period ends when screen failure status is determined.

##### **8.1.4.1. Reporting SAEs to Pfizer Safety**

All SAEs occurring in a subject during the active collection period are reported to Pfizer Safety on the CT SAE Report Form.

SAEs occurring in a subject after the active collection period has ended are reported to Pfizer Safety if the investigator becomes aware of them; at a minimum, all SAEs that the investigator believes have at least a reasonable possibility of being related to investigational product must be reported to Pfizer Safety.

Follow up by the investigator continues throughout and after the active collection period and until the event or its sequelae resolve or stabilize at a level acceptable to the investigator, and Pfizer concurs with that assessment.

##### **8.1.4.2. Recording Non-serious AEs and SAEs on the CRF**

During the active collection period, both non-serious AEs and SAEs are recorded on the CRF.

Follow-up by the investigator may be required until the event or its sequelae resolve or stabilize at a level acceptable to the investigator, and Pfizer concurs with that assessment.

#### **8.1.5. Causality Assessment**

The investigator’s assessment of causality must be provided for all AEs (serious and non-serious); the investigator must record the causal relationship on the CRF, and report such an assessment in accordance with the SAE reporting requirements, if applicable. An investigator’s causality assessment is the determination of whether there exists a reasonable possibility that the investigational product caused or contributed to an AE; generally the facts (evidence) or arguments to suggest a causal relationship should be provided. If the investigator does not know whether or not the investigational product caused the event, then the event will be handled as “related to investigational product” for reporting purposes, as defined by the sponsor. If the investigator's causality assessment is “unknown but not related” to investigational product, this should be clearly documented on study records.

In addition, if the investigator determines that an SAE is associated with study procedures, the investigator must record this causal relationship in the source documents and CRF, and report such an assessment in the dedicated section of the CT SAE Report Form and in accordance with the SAE reporting requirements.

#### **8.1.6. Sponsor's Reporting Requirements to Regulatory Authorities**

AE reporting, including suspected unexpected serious adverse reactions, will be carried out in accordance with applicable local regulations.

### **8.2. Definitions**

#### **8.2.1. Adverse Events**

An AE is any untoward medical occurrence in a study subject administered a product or medical device; the event need not necessarily have a causal relationship with the treatment or usage. Examples of AEs include, but are not limited to:

- Abnormal test findings;
- Clinically significant signs and symptoms;
- Changes in physical examination findings;
- Hypersensitivity;
- Progression/worsening of underlying disease;
- Drug abuse;
- Drug dependency.

Additionally, AEs may include signs and symptoms resulting from:

- Drug overdose;
- Drug withdrawal;
- Drug misuse;
- Drug interactions;
- Extravasation;
- Exposure during pregnancy (EDP);
- Exposure via breastfeeding;
- Medication error;

- Occupational exposure.

### **8.2.2. Abnormal Test Findings**

Abnormal objective test findings should be recorded as AEs when any of the following conditions are met:

- Test result is associated with accompanying symptoms; and/or
- Test result requires additional diagnostic testing or medical/surgical intervention; and/or
- Test result leads to a change in study dosing (outside of any protocol-specified dose adjustments) or discontinuation from the study, significant additional concomitant drug treatment, or other therapy; and/or
- Test result is considered to be an AE by the investigator or sponsor.

Merely repeating an abnormal test, in the absence of any of the above conditions, does not constitute an AE. Any abnormal test result that is determined to be an error does not require recording as an AE.

### **8.2.3. Serious Adverse Events**

A serious adverse event is any untoward medical occurrence at any dose that:

- Results in death;
- Is life-threatening (immediate risk of death);
- Requires inpatient hospitalization or prolongation of existing hospitalization;
- Results in persistent or significant disability/incapacity (substantial disruption of the ability to conduct normal life functions);
- Results in congenital anomaly/birth defect.

Or that is considered to be:

- An important medical event.

Medical and scientific judgment is exercised in determining whether an event is an important medical event. An important medical event may not be immediately life-threatening and/or result in death or hospitalization. However, if it is determined that the event may jeopardize the subject or may require intervention to prevent one of the other AE outcomes, the important medical event should be reported as serious.

Examples of such events are intensive treatment in an emergency room or at home for allergic bronchospasm; blood dyscrasias or convulsions that do not result in hospitalization; or development of drug dependency or drug abuse.

#### **8.2.4. Hospitalization**

Hospitalization is defined as any initial admission (even less than 24 hours) in a hospital or equivalent healthcare facility, or any prolongation of an existing admission. Admission also includes transfer within the hospital to an acute/intensive care unit (eg, from the psychiatric wing to a medical floor, medical floor to a coronary care unit, or neurological floor to a tuberculosis unit). An emergency room visit does not necessarily constitute a hospitalization; however, the event leading to the emergency room visit is assessed for medical importance.

Hospitalization does not include the following:

- Rehabilitation facilities;
- Hospice facilities;
- Respite care (eg, caregiver relief);
- Skilled nursing facilities;
- Nursing homes;
- Same-day surgeries (as outpatient/same-day/ambulatory procedures).

Hospitalization or prolongation of hospitalization in the absence of a precipitating clinical AE is not in itself an SAE. Examples include:

- Admission for treatment of a preexisting condition not associated with the development of a new AE or with a worsening of the preexisting condition (eg, for workup of a persistent pretreatment laboratory abnormality);
- Social admission (eg, subject has no place to sleep);
- Administrative admission (eg, for yearly physical examination);
- Protocol-specified admission during a study (eg, for a procedure required by the study protocol);
- Optional admission not associated with a precipitating clinical AE (eg, for elective cosmetic surgery);
- Hospitalization for observation without a medical AE;
- Preplanned treatments or surgical procedures. These should be noted in the baseline documentation for the entire protocol and/or for the individual subject.

Diagnostic and therapeutic noninvasive and invasive procedures, such as surgery, should not be reported as SAEs. However, the medical condition for which the procedure was performed should be reported if it meets the definition of an SAE. For example, an acute appendicitis that begins during the reporting period should be reported if the SAE requirements are met, and the resulting appendectomy should be recorded as treatment of the AE.

### 8.3. Severity Assessment

If required on the AE page of the CRF, the investigator will use the adjectives MILD, MODERATE, or SEVERE to describe the maximum intensity of the AE. For purposes of consistency, these intensity grades are defined as follows:	
MILD	Does not interfere with subject's usual function.
MODERATE	Interferes to some extent with subject's usual function.
SEVERE	Interferes significantly with subject's usual function.

Note the distinction between the severity and the seriousness of an AE. A severe event is not necessarily an SAE. For example, a headache may be severe (interferes significantly with the subject's usual function) but would not be classified as serious unless it met one of the criteria for SAEs, listed above.

### 8.4. Special Situations

#### 8.4.1. Protocol-Specified Serious Adverse Events

There are no protocol-specified SAEs in this study. All SAEs will be reported to Pfizer Safety by the investigator as described in previous sections, and will be handled as SAEs in the safety database.

#### 8.4.2. Potential Cases of Drug-Induced Liver Injury

Humans exposed to a drug who show no sign of liver injury (as determined by elevations in transaminases) are termed "tolerators," while those who show transient liver injury, but adapt are termed "adaptors." In some subjects, transaminase elevations are a harbinger of a more serious potential outcome. These subjects fail to adapt and therefore are "susceptible" to progressive and serious liver injury, commonly referred to as drug-induced liver injury (DILI). Subjects who experience a transaminase elevation above 3 times the upper limit of normal ( $\times$  ULN) should be monitored more frequently to determine if they are an "adaptor" or are "susceptible."

In the majority of DILI cases, elevations in aspartate aminotransferase (AST) and/or alanine aminotransferase (ALT) precede total bilirubin (TBili) elevations ( $>2 \times$  ULN) by several days or weeks. The increase in TBili typically occurs while AST/ALT is/are still elevated above  $3 \times$  ULN (ie, AST/ALT and TBili values will be elevated within the same lab sample). In rare instances, by the time TBili elevations are detected, AST/ALT values might have decreased. This occurrence is still regarded as a potential DILI. Therefore, abnormal elevations in either AST OR ALT in addition to TBili that meet the criteria outlined below

are considered potential DILI (assessed per Hy's law criteria) cases and should always be considered important medical events, even before all other possible causes of liver injury have been excluded.

The threshold of laboratory abnormalities for a potential DILI case depends on the subject's individual baseline values and underlying conditions. Subjects who present with the following laboratory abnormalities should be evaluated further as potential DILI (Hy's law) cases to definitively determine the etiology of the abnormal laboratory values:

- Subjects with AST/ALT and TBili baseline values within the normal range who subsequently present with AST OR ALT values  $>3 \times \text{ULN}$  AND a TBili value  $>2 \times \text{ULN}$  with no evidence of hemolysis and an alkaline phosphatase value  $<2 \times \text{ULN}$  or not available;
- For subjects with baseline AST **OR** ALT **OR** TBili values above the ULN, the following threshold values are used in the definition mentioned above, as needed, depending on which values are above the ULN at baseline:
  - Preexisting AST or ALT baseline values above the normal range: AST or ALT values  $>2$  times the baseline values AND  $>3 \times \text{ULN}$ ; or  $>8 \times \text{ULN}$  (whichever is smaller).
  - Preexisting values of TBili above the normal range: TBili level increased from baseline value by an amount of at least  $1 \times \text{ULN}$  or if the value reaches  $>3 \times \text{ULN}$  (whichever is smaller).

Rises in AST/ALT and TBili separated by more than a few weeks should be assessed individually based on clinical judgment; any case where uncertainty remains as to whether it represents a potential Hy's law case should be reviewed with the sponsor.

The subject should return to the investigator site and be evaluated as soon as possible, preferably within 48 hours from awareness of the abnormal results. This evaluation should include laboratory tests, detailed history, and physical assessment.

In addition to repeating measurements of AST and ALT and TBili, laboratory tests should include albumin, creatine kinase (CK), direct and indirect bilirubin, gamma-glutamyl transferase (GGT), prothrombin time (PT)/international normalized ratio (INR), total bile acids, alkaline phosphatase and acetaminophen drug and/or protein adduct levels.

Consideration should also be given to drawing a separate tube of clotted blood and an anticoagulated tube of blood for further testing, as needed, for further contemporaneous analyses at the time of the recognized initial abnormalities to determine etiology. A detailed history, including relevant information, such as review of ethanol, acetaminophen (either by itself or as a co-formulated product in prescription or over-the-counter medications), recreational drug, supplement (herbal) use and consumption, family history, sexual history, travel history, history of contact with a jaundiced person, surgery, blood transfusion, history of liver or allergic disease, and potential occupational exposure to chemicals, should be

collected. Further testing for acute hepatitis A, B, C, D, and E infection and liver imaging (eg, biliary tract) may be warranted.

All cases demonstrated on repeat testing as meeting the laboratory criteria of AST/ALT and TBili elevation defined above should be considered potential DILI (Hy's law) cases if no other reason for the liver function test (LFT) abnormalities has yet been found. **Such potential DILI (Hy's law) cases are to be reported as SAEs, irrespective of availability of all the results of the investigations performed to determine etiology of the LFT abnormalities.**

A potential DILI (Hy's law) case becomes a confirmed case only after all results of reasonable investigations have been received and have excluded an alternative etiology.

#### **8.4.3. Exposure to the Investigational Product During Pregnancy or Breastfeeding, and Occupational Exposure**

Exposure to the investigational product under study during pregnancy or breastfeeding and occupational exposure are reportable to Pfizer Safety within 24 hours of investigator awareness.

##### **8.4.3.1. Exposure During Pregnancy**

For both unapproved/unlicensed products and for marketed products, an exposure during pregnancy (EDP) occurs if:

- A female becomes, or is found to be, pregnant either while receiving or having been exposed (eg, because of treatment or environmental exposure) to the investigational product; or the female becomes or is found to be pregnant after discontinuing and/or being exposed to the investigational product;
- An example of environmental exposure would be a case involving direct contact with a Pfizer product in a pregnant woman (eg, a nurse reports that she is pregnant and has been exposed to chemotherapeutic products);
- A male has been exposed (eg, because of treatment or environmental exposure) to the investigational product prior to or around the time of conception and/or is exposed during his partner's pregnancy.

If a subject or subject's partner becomes or is found to be pregnant during the subject's treatment with the investigational product, the investigator must report this information to Pfizer Safety on the CT SAE Report Form and an EDP supplemental form, regardless of whether an SAE has occurred. In addition, the investigator must submit information regarding environmental exposure to a Pfizer product in a pregnant woman (eg, a subject reports that she is pregnant and has been exposed to a cytotoxic product by inhalation or spillage) to Pfizer Safety using the EDP supplemental form. This must be done irrespective of whether an AE has occurred and within 24 hours of awareness of the exposure. The information submitted should include the anticipated date of delivery (see below for information related to termination of pregnancy).

Follow-up is conducted to obtain general information on the pregnancy and its outcome for all EDP reports with an unknown outcome. The investigator will follow the pregnancy until completion (or until pregnancy termination) and notify Pfizer Safety of the outcome as a follow-up to the initial EDP supplemental form. In the case of a live birth, the structural integrity of the neonate can be assessed at the time of birth. In the event of a termination, the reason(s) for termination should be specified and, if clinically possible, the structural integrity of the terminated fetus should be assessed by gross visual inspection (unless pre-procedure test findings are conclusive for a congenital anomaly and the findings are reported).

If the outcome of the pregnancy meets the criteria for an SAE (ie, ectopic pregnancy, spontaneous abortion, intrauterine fetal demise, neonatal death, or congenital anomaly [in a live-born baby, a terminated fetus, an intrauterine fetal demise, or a neonatal death]), the investigator should follow the procedures for reporting SAEs.

Additional information about pregnancy outcomes that are reported to Pfizer Safety as SAEs follows:

- Spontaneous abortion includes miscarriage and missed abortion;
- Neonatal deaths that occur within 1 month of birth should be reported, without regard to causality, as SAEs. In addition, infant deaths after 1 month should be reported as SAEs when the investigator assesses the infant death as related or possibly related to exposure to the investigational product;

Additional information regarding the EDP may be requested by the sponsor. Further follow-up of birth outcomes will be handled on a case-by-case basis (eg, follow-up on preterm infants to identify developmental delays). In the case of paternal exposure, the investigator will provide the subject with the Pregnant Partner Release of Information Form to deliver to his partner. The investigator must document in the source documents that the subject was given the Pregnant Partner Release of Information Form to provide to his partner.

#### **8.4.3.2. Exposure During Breastfeeding**

Scenarios of exposure during breastfeeding must be reported, irrespective of the presence of an associated SAE, to Pfizer Safety within 24 hours of the investigator's awareness, using the CT SAE Report Form. An exposure during breastfeeding report is not created when a Pfizer drug specifically approved for use in breastfeeding women (eg, vitamins) is administered in accord with authorized use. However, if the infant experiences an SAE associated with such a drug's administration, the SAE is reported together with the exposure during breastfeeding.

#### **8.4.3.3. Occupational Exposure**

An occupational exposure occurs when, during the performance of job duties, a person (whether a healthcare professional or otherwise) gets in unplanned direct contact with the product, which may or may not lead to the occurrence of an AE.

An occupational exposure is reported to Pfizer Safety within 24 hours of the investigator's awareness, using the CT SAE Report Form, regardless of whether there is an associated SAE. Since the information does not pertain to a subject enrolled in the study, the information is not recorded on a CRF; however, a copy of the completed CT SAE Report Form is maintained in the investigator site file.

#### 8.4.4. Medication Errors

Other exposures to the investigational product under study may occur in clinical trial settings, such as medication errors.

Safety Event	Recorded on the CRF	Reported on the CT SAE Report Form to Pfizer Safety Within 24 Hours of Awareness
Medication errors	All (regardless of whether associated with an AE)	Only if associated with an SAE

##### 8.4.4.1. Medication Errors

Medication errors may result from the administration or consumption of the investigational product by the wrong subject, or at the wrong time, or at the wrong dosage strength.

Medication errors include:

- Medication errors involving subject exposure to the investigational product;
- Potential medication errors or uses outside of what is foreseen in the protocol that do or do not involve the participating subject;
- Refer to [Section 5.4](#) for examples of medication errors related to compliance with investigational product.

Such medication errors occurring to a study participant are to be captured on the medication error page of the CRF, which is a specific version of the AE page.

In the event of a medication dosing error, the sponsor should be notified immediately.

Whether or not the medication error is accompanied by an AE, as determined by the investigator, the medication error is recorded on the medication error page of the CRF and, if applicable, any associated AE(s), serious and non-serious, are recorded on an AE page of the CRF.

Medication errors should be reported to Pfizer Safety within 24 hours on a CT SAE Report Form only **when associated with an SAE**.

## 9. DATA ANALYSIS/STATISTICAL METHODS

Detailed methodology for summary and statistical analyses of the data collected in this study is outlined here and further detailed in a statistical analysis plan (SAP), which will be maintained by the sponsor. The SAP may modify what is outlined in the protocol where appropriate; however, any major modifications of the co-primary endpoint definitions or their analyses will also be reflected in a protocol amendment.

### 9.1. Sample Size Determination

A total of 600 subjects with 200 receiving PF-04965842 200 mg QD, 200 receiving PF-04965842 100 mg QD, and 200 receiving placebo (1:1:1 randomization) will provide 94% power to detect a ratio of median time to flare of at least 1.5 times between either dose of PF-04965842 (200 mg or 100 mg) and placebo. The Type I error rate is set at 5% (2-sided). Assuming based on prior data, that about 44% of subjects would meet the protocol-defined criteria to be a responder at Week 12, approximately 1370 subjects would need to enter the open label run-in period of the study to ensure that 600 subjects are available for randomization.

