**Responder criteria** are defined as a) achieving an IGA of clear (0) or almost clear (1) (on a 5-point scale), b) a reduction from IGA baseline of  $\geq 2$  points, and c) reaching an EASI-75 response compared to baseline. Baseline is defined as the IGA score and EASI score obtained prior to dosing on Day 1. Subjects meeting all of the responder criteria may be eligible for randomization.

Subjects who do not reach the response threshold required for randomization are declared non-responders after completion of the open label run-in period. Non-responders are not eligible for randomization in the B7451014 study, but may choose to enroll into the PF-04965842 Long Term Extension (LTE) study B7451015 providing they remain eligible; otherwise they are permanently discontinued from treatment and enter the 4-week untreated follow-up period in B7451014.

Subjects with a positive clinical response to PF-04965842 induction treatment at the end of the 12-week open-label run-in period enter a 40 week, double-blind, maintenance treatment period in which they are randomized into 1 of 3 treatment arms in a 1:1:1 ratio:

1. 100 mg PF-04965842 QD;
2. 200 mg PF-04965842 QD;
3. Placebo.

Randomization is stratified by age category, ie, <18 years and ≥18 years. Eligible subjects must have a documented history of inadequate response with topical AD medications or have required systemic therapies for control of their disease.

Medicated topical and/or systemic standard of care therapies are not allowed during the open-label run-in and blinded treatment periods. Medicated topical therapy is defined as a topical product that contains an active pharmaceutical ingredient indicated for the treatment of AD (irrespective of whether it is available as an over-the-counter [OTC] or prescription only product).

Following completion of 40 weeks of blinded treatment, all subjects are assessed for eligibility to enter the PF-04965842 LTE study B7451015. If a subject discontinues prematurely or is not eligible or willing to participate in B7451015, then the subject enters the 4-week untreated follow-up period in B7451014.

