After completing the 12-week rescue period, eligible subjects may enter study B7451015. Subjects discontinuing early from treatment, or who are otherwise ineligible for the LTE study will undergo a 4 week follow-up period in B7451014.

The total study duration if a subject does not flare is 52 weeks (12 weeks open-label treatment + 40 weeks blinded treatment). The maximum study duration is up to 64 weeks. This would only be achieved if a subject flared on the last day of the maintenance treatment period (52 weeks +12 weeks rescue). If subjects do not intend to enroll in the LTE study, the above durations are extended by +4 weeks of an untreated follow-up period.

A full schedule of activities for the study is provided in [Appendix 7](#).

Sample Size Determination

A total of 600 subjects with 200 receiving PF-04965842 200 mg QD, 200 receiving PF-04965842 100 mg QD, and 200 receiving placebo (1:1:1 randomization) will provide 94% power to detect a ratio of median time to flare of at least 1.5 times between either dose of PF-04965842 (200 mg or 100 mg) and placebo. The Type I error rate is set at 5% (2-sided). Assuming that about 44% of subjects would meet the protocol-defined criteria to be a responder at Week 12, (based on prior data), approximately 1370 subjects would need to enter the open label run-in period of the study to ensure that 600 subjects are available for randomization.

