5.1. Hypotheses and Decision Rules

The statistical objective of the study is to characterize the loss of response within each randomized group after achieving response at Week 12 following open-label treatment with 200 mg QD PF-04965842.

There are six key hypotheses to be tested for each pairwise comparison between two PF-04965842 doses (200 mg QD and 100 mg QD) and placebo, for the primary and key secondary endpoints. For these hypotheses, the familywise Type-I error rate will be strongly controlled at 5% using a sequential, gatekeeping procedure.

The procedure will first test the hypothesis of no difference for the primary endpoint between 200 mg QD and placebo at 5% level of significance. If this hypothesis is rejected, statistical significance will be assessed for the hypothesis of no difference for the key secondary endpoint between 200 mg QD and placebo at 5% level of significance. If rejected, the procedure will continue with the hypothesis of no difference for the primary endpoint between 100 mg QD and placebo and if rejected, continuing with the hypothesis of no difference between 100 mg QD and placebo for the key secondary endpoint. Finally, if all the above hypotheses are rejected, the procedure will continue with the hypothesis of no difference between 200 mg QD and 100 mg QD for the primary endpoint and if rejected, continuing with the hypothesis of no difference between 200 mg QD and 100 mg QD for the key secondary endpoint. All tests will be conducted at 5% level of significance. Formal statistical significance for any subsequent tests specified in this test hierarchy will not be claimed if the previous hypothesis in the sequence has not been rejected.

Hypotheses for all other endpoints not described here are to be tested at the nominal 5% level, without making adjustments for multiple comparisons.

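### The 94% power quoted for either dose applies as stated only to 200 mg; under the fixed test sequence the 100 mg claim has about 88% (at most 89.6%) if both ratios are 1.5

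*Protocol*

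**What the plan says.** Protocol 9.1 plans 600 randomized subjects, 200 per arm, and states that this "will provide 94% power to detect a ratio of median time to flare of at least 1.5 times between either dose of PF-04965842" and placebo, naming both 200 mg and 100 mg. The test level is given as two-sided 5%. The Statistical Methods part of the protocol summary carries the same statement, and so does the sample size paragraph in SAP 2.2 ("will provide 94% power to detect a ratio of median time to flare of at least 1.5 times"). None of the three places mentions the order of testing. None gives an event count, a placebo median or a dropout rate.

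Protocol 9.2.2 and SAP 5.1 set out six tests in a fixed order, each at 5%, with no formal claim after a test that fails. The order begins:

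1. 200 mg against placebo, primary endpoint (flare).
2. 200 mg against placebo, key secondary endpoint (IGA of 2 or higher).
3. 100 mg against placebo, primary endpoint. SAP 5.1: "If rejected, the procedure will continue with the hypothesis of no difference for the primary endpoint between 100 mg QD and placebo".

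The 100 mg key secondary test and the two 200 mg against 100 mg tests follow. Neither document gives the power of the third step under this sequence.

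**The concern.** A reader of Protocol 9.1 would expect a 94% chance of a confirmatory 100 mg result if the true median ratio is 1.5. The testing rule makes that result depend on three rejections, not one. If 94% is the power of a single comparison, the design delivers it for 200 mg, which is tested first. It cannot deliver quite as much for 100 mg at the same effect. What is at stake is the accuracy of the stated chance of a formal claim for the lower dose. Type I error control is not affected.

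**Working it through.** **Inputs.** From Protocol 9.1: 94% power, two-sided 5%, median ratio 1.5, 200 per arm with one shared placebo arm. From the study design: 40 weeks of blinded treatment. From Protocol 9.2.2 and SAP 5.1: the order of tests. Assumed, because not stated: exponential event times (so the hazard ratio is 1/1.5 = 0.667), no dropout, and, where needed, a placebo median of 16 weeks.

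**1. The plan's own figure as a single comparison.** The Schoenfeld formula gives the flares needed in one drug-placebo pair:

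d = 4(z₀.₉₇₅ + z₀.₉₄)² / (ln 1.5)² = 4(1.960 + 1.555)² / 0.4055² ≈ 301.

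That is 301/400 ≈ 75% of the pair. With assumed medians of 16 weeks on placebo and 24 on drug, the expected flares in 40 weeks are 200(1 − 2^(−40/16)) + 200(1 − 2^(−40/24)) = 164.6 + 137.0 ≈ 302, and the power is 94.1%. Assumed placebo medians of 12, 20 and 24 weeks give 96.1%, 91.6% and 88.7%. So 94% is attainable as a per-comparison power, but it cannot be derived from the inputs given. The 301 flares are back-solved from 94% and are not a planning number in either document.

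**2. Both primary tests significant, both ratios 1.5.** The two log-rank statistics share the placebo arm. With equal allocation and similar event numbers per arm, their correlation is (1/d₀)/(1/d₀ + 1/d₁) ≈ 0.5. It is slightly lower when placebo has more events. Taking 94% for each test:

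P(both Z > 1.96) = Φ₂(1.555, 1.555; ρ = 0.5) = 0.896.

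- At ρ = 0.45 the result is 0.894.
- If the tests were independent it would be 0.94² = 0.884.
- A log-rank simulation of 20,000 trials (medians 16, 24 and 24 weeks) gave marginal powers of 0.939 and 0.940, correlation 0.49 and joint power 0.894.

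This step needs the stated 94%, the shared placebo arm and equal ratios. It does not need the missing event count. The intervening key secondary test can only lower the result, so 89.6% is a ceiling in this scenario.

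**3. Adding the 200 mg key secondary test.** Flare requires an IGA of 2 or higher, and SAP 6.2.1.1 observes IGA up to the first day of rescue. Every flare is therefore also a key secondary event, at the same time or earlier. A simulation that respects this nesting used ratio 1.5 on both endpoints, placebo flare median 16 weeks, 40 weeks and no dropout. It added a hazard of 25% to 100% of the flare hazard for IGA of 2 or higher without flare. The 200 mg key secondary test then had roughly 96% to 97% power, and all three tests succeeded in about 88% of trials.

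**4. A stronger 200 mg effect, with 100 mg kept at 1.5.** A 200 mg ratio of 1.75 gives joint power of about 93.7% for the two primary tests, and 2.0 gives about 93.9%. With 1.75 on both endpoints, all three tests succeed in about 94%.

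| True ratios (200 mg / 100 mg) | Two primary tests | All three tests |
|---|---|---|
| 1.5 / 1.5 | at most 89.6% | about 88% |
| 1.75 / 1.5 | about 93.7% | about 94% |

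At equal ratios the chance of missing a 100 mg claim is therefore about 12% (at least 10.4%), against the 6% that the sentence suggests.

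**The case against.** The strongest reply is that the sentence describes power to detect a given ratio between a dose and placebo. That is a per-comparison statement, it can be true as such, and quoting it beside a hierarchy is common. This stands: the figure is incompletely described and not shown to be miscalculated.

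The second reply is that equal effects are not what the sponsor expects. Protocol 1.6 expects the 100 mg dose to differ from 200 mg in efficacy. The phase 2b results in Protocol 1.2.4 show a dose response (IGA response 44.5% against 27.8%; EASI-75 63.7% against 41.6%). If 100 mg has a ratio of 1.5, the 200 mg ratio is then probably larger and the earlier tests cost little. This also stands, and it limits the size of the point. But Protocol 9.1 applies one ratio to both doses and states no larger 200 mg effect.

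Third, 94% might already be a joint power. That would need about 96.7% per comparison, or about 350 flares in 400 subjects (88%). Nothing in the text suggests it, but the calculation is not shown and it cannot be excluded. In that case too the sentence should say what it means.

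A reader might also infer that 100 mg power could fall into the range of 75% to 84%, by supposing that the 200 mg key secondary test has only 80% to 90% power. The documents do not support this. Because every flare is also a key secondary event, that test has at least as many events as the primary, and at the same ratio its power is normally no lower. A figure in that range would need a weaker effect on IGA of 2 or higher, which neither document suggests.

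**Conclusion.** The point holds as one of labelling and completeness. Read per comparison, 94% describes the first test in the sequence only. With both ratios at 1.5, power to claim 100 mg on the primary endpoint is at most about 89.6%. It is about 88% with the 200 mg key secondary test included. The 89.6% rests on taking the stated 94% as per comparison, on a correlation of about 0.5 and on equal ratios. The 88% also assumes the same ratio on IGA of 2 or higher, exponential times, a 16-week placebo median and no dropout. With a clearly larger 200 mg effect the figure returns to about 94%.

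A reader might infer that the sample size is wrong or that the testing procedure is faulty. Neither follows. The sequence controls the familywise error as described, and 94% is attainable for a single comparison with 200 per arm. The absence of a stated power for the key secondary test is missing detail, not a separate fault.

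**What to change.** In Protocol 9.1, the Statistical Methods part of the protocol summary and SAP 2.2, state that:

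- 94% is the power of each drug-placebo comparison taken alone;
- under the testing sequence, power to claim 100 mg on the primary endpoint is about 88% (at most 89.6%) when both median ratios are 1.5, and approaches 94% if 200 mg is more effective;
- these figures rest on named assumptions: placebo median, dropout, and the ratio assumed for the key secondary endpoint. If the sponsor's planning values differ from those used here, the 88% should be recomputed with them.

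If 94% was in fact a joint power, say so and give the event count behind it.

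The cost is a sentence or two in each place and a slightly less favourable figure for 100 mg. Sample size, test order and analysis stay as they are. Appendix 3 of the protocol already refers to enrollment as complete, so the change affects only how the design is described.
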